11.4. Optional Pharmacogenomic Assessment

Patients who meet all criteria for randomization will be eligible to participate in the pharmacogenomic assessment. A single blood draw will be collected in one 6mL K2 EDTA tube for each participating patient after they have signed a separate ICF for pharmacogenomic

assessment. The blood draw for this assessment can be done at any in-clinic visit post-Screening; however, it is preferred that the sample is collected at Baseline (Visit 2) whenever possible. The blood draw may only be performed after the patient has been confirmed to meet all criteria for randomization, and after the patient has reviewed and signed the separate pharmacogenomic testing ICF.

The purpose of this testing is to allow genetic sequencing and analysis for genetic variants related to treatment response to TNX-601 ER. It is presumed that unused sample will be stored up to 15 years, and potentially utilized to develop a pharmacogenomic test for determining likelihood of treatment response to TNX-601 ER. A decision not to participate in optional pharmacogenomic testing will not affect the patient's eligibility for the main study. Patients have the right to stop participating at any time during the study or during the time of sample storage, and, if a patient decides to withdraw from the pharmacogenomics portion of this study, any remaining sample will be destroyed and not used for further research. Data collected before a patient's withdrawal from the pharmacogenomics portion of this study will remain in the research database.

12. DEFINITIONS, RECORDING, AND REPORTING OF ADVERSE EVENTS

12.1. Definition of Adverse Events

According to International Conference on Harmonization (ICH) guidance E2A, Clinical Safety Data Management: Definitions and Standards for Expedited Reporting, an adverse event (AE) is any untoward medical occurrence in a patient or clinical investigation patient administered a pharmaceutical product and which is not necessarily required to have a causal relationship with this treatment. An AE can therefore be any unfavorable and unintended sign (including an abnormal laboratory finding, for example), symptom, or disease temporally associated with the use of a study drug, whether or not considered related to the study drug.

A treatment-emergent AE (TEAE) is an AE that either commenced following initiation of study drug or was present prior to study drug but increased in frequency or severity following initiation of study treatment.

12.2. Adverse Event Recording

12.2.1. Coding the Adverse Event

Standard medical terminology should be used in describing AEs. MedDRA[®] will be used as the standard coding dictionary for AEs and in describing the patient's medical history, and the World Health Organization (WHO) Drug Dictionary will be used to code concomitant medications. Informal descriptions should be avoided.

12.2.2. Severity of Adverse Event

AEs should be graded as mild, moderate, or severe using the following definitions.

- *Mild:* Awareness of signs or symptoms, but easily tolerated and of minor irritant type causing no loss of time from normal activities. Symptoms do not require therapy or a medical evaluation; signs and symptoms are transient.
- *Moderate:* Events introduce a low level of inconvenience or concern to the patient and may interfere with daily activities but are usually improved by simple therapeutic measures; moderate experiences may cause some interference with functioning.
- *Severe:* Events interrupt the patient's normal daily activities and generally require systemic drug therapy or other treatment; they are usually incapacitating.

To make sure there is no confusion or misunderstanding of the difference between the terms "serious" and "severe," which are not synonymous, the following note of clarification is provided. The term "severe" is often used to describe the intensity (severity) of a specific event (as in mild, moderate, or severe myocardial infarction); the event itself, however, maybe of relatively minor medical significance (such as severe headache). This is not the same as "serious," which is based on patient/event outcome or action criteria usually associated with events that pose a threat to a patient's life or functioning. Seriousness (not severity) serves as a guide for defining regulatory reporting obligations.

12.2.3. Relationship of Adverse Events (AEs) to Study Drug

The Investigator will assess the potential relationship of the AE to study drug using the following descriptions.

- *Not Related:* This category applies to an AE that is clearly not related to the investigational agent/procedure, beyond a reasonable doubt. That is, another cause of the event is most plausible; and/or a clinically plausible temporal sequence is inconsistent with the onset of the event and the administration of study drug and/or a causal relationship is considered biologically implausible.
- *Unlikely Related:* This category applies to an AE that could reasonably be considered caused by something else, and where there is no known or expected response pattern to the suspected study drug.
- *Possibly Related:* This category applies to an AE that follows a reasonable temporal sequence from administration of the study drug and that follows a known or expected response pattern to the suspected study drug, but that could readily have been produced by a number of other factors.

12.3. Serious Adverse Events (SAEs) and Serious Adverse Drug Reactions

Any SAE that occurs at any time during the study, including a clinically significantly abnormal laboratory test result that is considered serious, must be reported to Tonix or its designee(s) so that Tonix may comply with regulatory obligations. For these and all other SAEs, an SAE report form must be completed and sent by facsimile or email to Tonix or its designee(s) within 24 hours of the site's initial awareness of the event. These requirements apply equally to all patients, regardless of the study phase or the at-risk patient's treatment assignment or dosage.

A serious adverse event (experience) or reaction is any untoward medical occurrence that, at any dose:

- Results in death,
- Is life-threatening,
- Requires in-patient hospitalization or prolongation of existing hospitalization,
- Results in persistent or significant disability/incapacity,
- Is a congenital anomaly/birth defect, or
- Is an important medical event

NOTE: The term "life-threatening" in the definition of "serious" refers to an event in which the patient was at risk of death at the time of the event. It does not refer to an event that hypothetically might have caused death if it were more severe.

Medical and scientific judgment should be exercised in deciding whether expedited reporting is appropriate in other situations, such as important medical events that may not be immediately life-threatening or result in death or hospitalization but may jeopardize the patient or may require intervention to prevent one of the other outcomes listed in the definition above. These should also usually be considered serious. Examples of such events are intensive treatment in an emergency room or at home for allergic bronchospasm, blood dyscrasias or convulsions that do not result in hospitalization, or development of drug dependency or drug abuse.

A death occurring during the study, during the per-protocol follow-up period, or reported to the Investigator after study participation must be reported to Tonix or its designee(s) immediately, whether or not it is considered treatment-related.

SAEs report forms must be submitted to the site/investigator's awareness of the event via facsimile or email:

within 24 hours of

For questions pertaining to the reporting of SAEs or the completion of SAE documentation, site personnel should call the

Initial SAE reports must be followed by detailed descriptions. These may include copies of hospital case records and other documents when requested. All facsimile and email submissions will be confirmed by Rho Product Safety within 1 business day of receipt.

As noted above, all SAEs need to be initially reported to Rho Pharmacovigilance. The study Medical Monitors are available to discuss any SAEs or other AEs of concern with sites and investigators as needed.

Contact information for the Medical Monitors is provided below:

 Table 3:
 Medical Monitoring Contact Information

The Investigator, or the sponsor or designee in the case of a central Institutional Review Board (IRB), also must notify the Ethics Committee (EC)/IRB of the occurrence of the SAE, in writing, as soon as is practicable and in accordance with local law. A copy of this notification must be provided to Tonix or its designee.

In the event of an SAE that meets the criteria for expedited reporting, an Investigational New Drug (IND) Safety Report will be prepared for submission to the Food and Drug Administration (FDA).

12.4. Pregnancy

All pregnancies occurring during the study (after exposure to study drug) or within 28 days after discontinuation of study drug must be followed until resolution (ie, birth or voluntary or spontaneous termination of the pregnancy) and reported within 24 hours of the site's awareness to Tonix and/or its designee. Any patient found to be pregnant at any time during the study will be withdrawn from the study immediately. Any pregnancy outcome that meets the criteria for an SAE will be reported as an SAE.

13. STATISTICS

A full description of the statistical analyses to be performed at study completion will be provided in a Statistical Analysis Plan (SAP) prior to unblinding.

Baseline (Visit 2) will be defined as those values recorded closest to, but prior to administration of the first dose of study drug.

Unless otherwise noted, significance tests of treatment differences will be tested at the two-sided 0.05 level.

13.1. Populations for Analysis

The following populations will be defined for use in analyzing the efficacy and safety data in the study (see SAP for more details):

- Safety Population (SAFETY): All patients who receive at least 1 dose of the investigational product. All safety analyses and demographic/baseline characterization will be performed using this population, analyzed as treated.
- Intention-to-Treat Population (ITT): All randomized patients who receive at least 1 dose of the investigational product. This is the primary population for efficacy analyses and patients will be analyzed based on their randomized treatment.

13.2. Estimate of Sample Size

The sample size will be approximately 300 patients with MDD.

13.3. Assessment of Demographic and Baseline Characteristics

Demographic and baseline characteristics such as age, gender, race/ethnicity, height, weight, BMI, education, employment status, and smoking history will be summarized by treatment group (TNX-601 ER and placebo) and overall using descriptive statistics.

Medical History will be coded using MedDRA and summarized by SOC and Preferred Term using frequency counts by treatment group.

13.4. Efficacy Analysis

13.4.1. Efficacy Endpoints

Primary Efficacy Endpoint:

The primary efficacy endpoint will be the change from baseline in the MADRS total score at Week 6.

Key Secondary Efficacy Endpoints: The efficacy endpoints listed below are considered key secondary endpoints.

- Change from Baseline (Visit 2) in the CGI-S score at Week 6
- Change from Baseline (Visit 2) in the SDS total score at Week 6

Exploratory Endpoints:

- Proportion of patients achieving response, defined as a ≥50% decrease from Baseline (Visit 2) in MADRS total score, assessed at Weeks 2, 4, and 6
- Proportion of patients in remission, defined as a MADRS total score <=10 at Weeks 2,4, and
 6
- Proportion of patients achieving sustained response, defined as a ≥50% decrease from Baseline (Visit 2) in MADRS total score at Weeks 4 and 6
- •
- Proportion of patients with a CGI-I rating of "very much improved" or "much improved" at Weeks 2, 4, and 6
- Mean CGI-I score at Weeks 2, 4, and 6
- Change from Baseline (Visit 2) in PGIS score at Weeks 2, 4, and 6
- Proportion of patients with a PGIC rating of "very much improved" or "much improved" at Weeks 2, 4, and 6
- Mean PGIC score at Weeks 2, 4, and 6
- Change from Baseline (Visit 2) to Week 6 in the CSFQ-14 total score in females and in males (analyzed separately)
- Change from Baseline (Visit 2) in the MADRS total score at Week 2 and Week 4
- Change from Baseline (Visit 2) in the CGI-S score at Week 2 and Week 4
- Change from Baseline (Visit 2) in the SDS total score at Week 2 and Week 4
- Change from Baseline (Visit 2) in the HARS total score at Weeks 2, 4, and 6
- Change from Baseline (Visit 2) in each of the 3 domains (work/school; social life; home life or family responsibilities) using the SDS at Weeks 2, 4, and 6
- Proportion of patients with a CGI-S rating of "normal, not at all ill" or "borderline mentally ill" at Weeks 2, 4, and 6
- Proportion of patients with a PGIS rating of "not present", "very mild", or "mild" at Weeks 2, 4, and 6

13.4.2. Primary Efficacy Estimand

Population

The analysis population will be ITT patients with MDD as defined by the protocol inclusion/exclusion criteria.

Variable

The primary endpoint will be the change from Baseline (Visit 2) to Week 6 in the MADRS total score.

Intercurrent Events

Concomitant medications and all other intercurrent events other than discontinuation will use a treatment policy strategy; data will be analyzed as observed. A hypothetical strategy will be employed to handle intermittent missing data and discontinuation. Missing data will be imputed via MI, and details regarding the MI approach will be described in the SAP.

Population-Level Summary

The population-level summary will be the difference in least-square means between treatment arms (analyzed as randomized) at Week 6.

The primary efficacy analysis will use a mixed model repeated measures (MMRM) approach to estimate mean change from baseline to Week 6 in the MADRS total score visit in the TNX-601 ER and placebo arms. The model will include all patients in the ITT population, and the dependent variable will be the observed change from baseline in the MADRS total score at each post-randomization in-clinic visit. Covariates in the model will include the fixed categorical effects of treatment, site, visit, and treatment by visit interaction, as well as the continuous fixed covariates of baseline score and baseline score by visit interaction. Missing data will be imputed via MI, and details regarding the MI approach will be described in the SAP.

The primary analysis will be followed by several sensitivity analyses. Further details on sensitivity analyses can be found in the SAP.

13.4.3. Key Secondary Efficacy Analyses

The key secondary efficacy endpoints will apply estimands parallel with the primary estimand, adjusted for the endpoint in question, but with identical populations and handling of intercurrent events. MMRM methodology will be utilized for the continuous secondary endpoints, and analyses will be based on the ITT population. The dependent variable will be the observed change from baseline in the respective secondary endpoint at each post-randomization visit. Covariates in the model will include the fixed categorical effects of treatment, site, visit, and treatment by visit interaction, as well as the continuous fixed covariates of baseline score and baseline score by visit interaction.

To adjust for multiplicity and to control for overall type I error, a sequential test procedure will be applied to the key secondary efficacy endpoints. If the primary analysis produces a result that is statistically significant, a nominal significance level will be used for comparing the secondary endpoints in an ordered fashion. If the analysis for a secondary endpoint does not produce a statistically significant result, then the remaining secondary endpoint analyses will automatically be considered non-significant regardless of the p-value produced. In the case of an increase in sample size, the same methodology/critical value used for the primary endpoint will be applied to the key secondary endpoints for the purposes of the sequential testing. The order in which the secondary endpoints are to be tested will be specified in the SAP.

No other adjustments for multiplicity will be made and other p-values displayed in the output will be considered for descriptive summary purposes only and will not be used for formal

inference. Full details regarding the statistical analyses for the listed endpoints will be provided in the SAP.

13.4.4. Exploratory Analyses

Exploratory efficacy analyses will be based on the ITT population. Details on exploratory efficacy analyses can be found in the SAP.

13.5. Safety Analyses

Safety analyses will be performed using the Safety Population. Safety and tolerability will be assessed by:

- Incidence of AEs and SAEs throughout the entire duration of the study
- Incidence of AEs associated with abuse liability using the MADDERS[®]
- Assessment of physical examination findings
- Changes from baseline (Visit 2) in ECG results
- Changes from baseline (Visit 2) in clinical laboratory test results
- Changes from baseline (Visit 2) in vital signs and weight
- Indications of increased suicidal ideation or behavior as assessed by the C-SSRS
- Changes from baseline (Visit 2) in patient-rated CSFQ-14 in males and in females, assessed separately
- Change from baseline Visit 5 or End of Treatment) in the SOWS at the safety follow-up visit

Adverse events will be coded using MedDRA and will be summarized overall and by preferred term and system organ class. Adverse events will also be summarized by severity and relationship to study drug. Serious AEs and AEs leading to discontinuation of study drug will also be summarized. Actual values and changes from baseline for responses on the CSFQ-14, and actual values and changes from baseline in clinical laboratory test results, ECG parameters, vital signs, and weight will be summarized using descriptive statistics (n, mean, SD, median, minimum, and maximum). AEs associated with abuse liability of the study drug will be evaluated using the MADDERS[®]. Withdrawal symptoms associated with the study drug after the End of Treatment (Visit 5/ET) will be evaluated using the SOWS.

The number of patients with suicidal behaviors, ideations and acts based on the C-SSRS will be tabulated by treatment group and listed. Physical examination data will be presented in data listings.

13.6. Interim Analyses

An interim analysis will be performed once approximately 50% of the planned patients have enrolled and those patients have either completed the study or discontinued early. The purpose of the interim will be to evaluate the study for futility and potentially increase the sample size to maintain statistical power conditioned on the results of the first 50% of patients. The study team

will only be informed of the recommendation to halt the study for futility, maintain the original sample size, or to increase the sample size (by a fixed, pre-specified amount). All recommendations by the statistical review committee are non-binding.

For the primary and key secondary outcomes, the results from before and after the interim will be combined with Cui, Hung, Wang (CHW) methodology (Cui, 1999). Full details of the interim analysis procedure and steps to maintain treatment blinding of the study team will be described in the SAP and the Interim Analysis Charter and finalized prior to execution of the interim analysis.

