8.1.4. Timing of Analyses

All final, planned analyses will be performed after the last participant has completed all study assessments, all relevant study data have been processed and integrated into the analysis database, and the database has been locked.

Any post-hoc, exploratory analyses completed to support planned study analysis, which were not identified in this SAP, will be documented and reported in appendices to the CSR. Any results from these unplanned analyses (post-hoc) will also be clearly identified in the text of the CSR.

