8.1.5. Multiple Comparisons/Multiplicity

The overall type I error rate will be controlled at α =0.05 for the set of primary and key secondary endpoint comparisons using a serial gatekeeping approach.

At each step, if a p-value fails to meet the alpha threshold for significance, the process will be halted and all subsequent comparisons declared non-significant. This will continue with the same pattern through the endpoints in the order listed below:

The order of the analyses will be:

- Change from Baseline (Visit 2) in the MADRS total score at Week 6 (Primary)
- Change from Baseline (Visit 2) in the CGI-S score at Week 6
- Change from Baseline (Visit 2) in the SDS total score at Week 6

Although all p-values will be non-significant following the first to fail to meet its alpha threshold, p-values will be reported for all the above endpoints; they will be noted as descriptive for those following the first non-significant p-value.

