9.1.2. Primary Analysis of the Primary Endpoint

Summary statistics (mean, SD, median, minimum, maximum) for the primary efficacy endpoint will be reported for the change from the Baseline to week 6 for each of the treatment groups. The change from Baseline will be analyzed in an MMRM model for each multiple imputation set with fixed effects of treatment, visit, baseline value, treatment by visit interaction, baseline by visit interaction and pooled site; an unstructured covariance matrix will be used. Sites with less than 5 patients will be pooled into a single site; this covariate may be removed from the model in the case of convergence issues. Least square means (LSMs), standard errors, and the LSM differences (treatment vs placebo) for each of the 20 MI repeats will be combined using SAS procedure MIANALYZE (Rubin, 1976) and 95% CIs and p-values will be reported for each. Denominator degrees of freedom will use the Kenward Rogers approach. Should the model with unstructured variance fail to converge using the default Newton-Raphson approach, the Fisher scores (via the SCORING option of the PROC MIXED statement) will be utilized. Should this also fail to converge, then other approaches as detailed in Lu 2010 will be utilized. Once these approaches have been exhausted, then the following structures will be used in order with the first to converge being selected: heterogeneous Toeplitz, heterogeneous first-order autoregressive, Toeplitz, first order autoregressive and compound symmetric will be attempted in that order; in these cases, the sandwich estimator (Diggle and Kenward 1994) will be used to estimate the standard errors of the fixed effects parameters and the denominator degrees of freedom will utilize the DDFM=BETWITHIN option in SAS®.

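### Does the plan leave open whether the CHW combination or a single MMRM decides the trial?

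*Protocol*

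**What the plan says.** - **Protocol 13.6** (and the synopsis) plans an interim analysis at about half of the planned enrolment. It can lead to a futility stop, no change, or a fixed increase in N. On the primary and both key secondaries it states that "the results from before and after the interim will be combined with Cui, Hung, Wang (CHW) methodology (Cui, 1999". No condition on the interim decision is attached. Details are deferred to the SAP and the Interim Analysis Charter.
- **Protocol 13.4.3** tests the key secondaries in order at a nominal level and adds: "In the case of an increase in sample size, the same methodology/critical value used for the primary endpoint will be applied".
- **Protocol 13.4.2** specifies an MMRM for the primary endpoint: "The model will include all patients in the ITT population".
- **SAP 9.1.2** fits that MMRM to each imputed data set. The estimates "for each of the 20 MI repeats will be combined using SAS procedure MIANALYZE", which yields the confidence intervals and p-values. On the site covariate: "Sites with less than 5 patients will be pooled into a single site". SAP 9.2.1 treats CGI-S and SDS the same way as the primary.
- **Error level.** SAP 8.1.5: "The overall type I error rate will be controlled at α =0.05 for the set of primary and key secondary endpoint comparisons". Protocol 13: "significance tests of treatment differences will be tested at the two-sided 0.05 level".

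Three parts of the released SAP are visibly incomplete. Section 8.1.1 (Study Success) is a heading without text. Section 12 (changes from the protocol) is empty. Section 9.1.1 lacks the staged imputation procedure that 9.1.3.1 says is described there.

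**The concern.** Read in sequence, these sections can seem to give three tests: CHW in all cases (13.6), a special method only after an increase in N (13.4.3), and one MMRM fit to everyone (13.4.2 and SAP 9.1.2). An analyst who opens SAP 9.1.2 finds a p-value with no stages, weights or combination step.

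The choice could matter. If the CHW components come from separate fits before and after the interim, then site effects, baseline slope and variance are estimated twice, and the combined Z is not the Z of one overall fit. After an increase in N, the two tests also weight the stages differently. A borderline MADRS result could pass one test and fail the other, and the gate to CGI-S and SDS would move with it. If the choice were made after unblinding, the error rate would no longer be fixed in advance.

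**Working it through.** **Reading the passages together**

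1. CHW is a way of combining stage results; the MMRM is a model that produces such results. The sentence in 13.4.2 about all ITT patients names the analysis population and does not rule out a combination step.
2. The sentence in 13.4.3 aligns the key secondaries with the primary after an increase. It does not say that the primary is tested differently without one. Its nominal level also fits 13.6: the interim has no efficacy stop and its recommendations are non-binding, so no alpha is spent and the critical value stays at 1.960 (two-sided 0.05).
3. SAP 8.1.4 says "All final, planned analyses will be performed after the last participant has completed all study assessments". This concerns the timing of final analyses and is no sign that the interim was dropped.

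**Inputs.** From the documents: N of about 300, interim at about 50% (so 150 + 150), two-sided 0.05. Assumed, because the documents do not give them: an increase of 75, 150 or 300 patients, and the rule that triggers it.

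**N unchanged**

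- CHW: Z = √0.5·Z1 + √0.5·Z2. Pooled: Z = √t·Z1 + √(1−t)·Z2, where t is the share of patients before the interim. The correlation is √(0.5t) + √(0.5(1−t)), which is 1.000 at t = 0.50, 0.9987 at 0.45 and 0.9949 at 0.40.
- If Z2 is the increment of the cumulative statistic, Z2 = (Z − √0.5·Z1)/√0.5, then at the planned even split CHW returns the overall Z exactly and disagreement is zero.
- If each stage is refitted separately, a simulation can size the gap. It used 20,000 trials per scenario, complete-data Week 6 ANCOVA in place of the MMRM, 30 uneven sites, and assumed SD of about 10, site SD 2 and baseline correlation 0.3. The correlation was 0.985, so the SD of the difference is √(2 × 0.015) = 0.17. Verdicts differed in 4.1% of trials at 80% power and 2.4% at 90%. Repeat simulations gave 3.6% to 3.7% near 80% power. Without the site covariate, which SAP 9.1.2 allows if convergence fails, the figure was 1.8%.
- Two-sided error under the null was 0.049 (pooled) and 0.048 (CHW). It reached 0.056 only if significance on either test were accepted.

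**N increased** (numerical integration over the interim Z under the null, critical value 1.960; conditional power under the current trend)

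| Rule for the increase (assumed) | +75 | +150 | +300 |
|---|---|---|---|
| CHW, any rule tried | 0.0500 | 0.0500 | 0.0500 |
| Pooled, conditional power 0.3 to 0.8 | 0.0496 | 0.0492 | 0.0486 |
| Pooled, conditional power 0.1 to 0.9 | 0.0498 | 0.0494 | 0.0487 |
| Pooled, least favourable rule | 0.0523 | 0.0539 | 0.0560 |

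Individual results can cross 1.96 in either direction. With 150 + 300 patients, the pooled weights are √(150/450) = 0.577 and √(300/450) = 0.816:

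- Z1 = 1.6, Z2 = 1.2: CHW = 0.707 × 2.8 = 1.980; pooled = 0.924 + 0.980 = 1.904.
- Z1 = 1.0, Z2 = 1.75: CHW = 0.707 × 2.75 = 1.945; pooled = 0.577 + 1.429 = 2.006.

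Such cases are rare. With the 0.3 to 0.8 zone and increases of 75 or 150, the tests disagree in about 0.6% to 1.0% of the trials in which N is raised.

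**The case for a change.** The strongest case for a change is that 13.6 sends the reader to the SAP, and the readable SAP leads to a p-value that is not visibly the CHW statistic. If CHW applied in every case, the condition in 13.4.3 about an increase in N would be unnecessary. With separate stage fits, about 1 trial in 25 at 80% power would change verdict with the choice. Naming the statistic before unblinding would cost some wording and two fits per endpoint.

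One part of this stands: no readable sentence says how the MMRM results feed the CHW combination, or how small sites are pooled within a stage. The rest is weaker.

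- The 1 in 25 depends on separate stage fits, which the documents do not specify.
- The 0.056 needs permission to count either test, which no passage gives.
- The 0.0523 to 0.0560 needs a trigger that the documents do not state.
- Missing weights or a missing critical value cannot be held against the plan when the relevant SAP sections are blank or cut and the Charter is not among the documents.

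Requiring CHW from stage-wise refits even when N is unchanged would correct no error, and it lowers simulated power from 79.8% to 78.9%. Reasonable statisticians differ on that choice.

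**Conclusion.** The concern does not call for a change. Protocol 13.6 names the combination method and the MMRM sections name the model. Protocol 13.4.3 keeps the key secondaries in step with the primary. What the readable text lacks is the sentence that joins them, a gap that the trial's analysts would fill from the full SAP and the Charter, to which 13.6 defers.

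Each test holds its level when N is unchanged. After an increase, CHW holds 0.0500 under every rule tried, and the pooled test stays at 0.0486 to 0.0498 in the two conditional-power zones tabulated. Verdicts differ in anything from none to about 4% of trials when N is unchanged, according to how the stage statistics are formed.

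These figures rest on an even split, on assumed increases and triggers, and on a complete-data ANCOVA in place of the MMRM with multiple imputation. A cross-reference from SAP 9.1.2 to Protocol 13.6 would help a reader of the released text, but it would alter no analysis.
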